### 4 STUDY DESIGN

#### 4.1 OVERALL DESIGN

This is a Stage I, single-site trial to test the feasibility and acceptability of a novel intervention, mPal, through a pilot randomized controlled trial. Patient components are randomized. Provider components are not randomized. mPal is a multilevel implementation strategy designed to educate patients and providers about palliative care, identify patient palliative care needs, and facilitate referrals to palliative care during advanced stage lung cancer treatment.

To accomplish study objectives, we will conduct a pilot randomized controlled trial of the mPal protocol with 60 advanced stage lung cancer patients (40 mPal; 40 usual care); 6 oncology providers will be recruited and receive the provider components of mPal. The primary feasibility outcome that will be tested is patient enrollment ( $\geq 60\%$ ). We will also collect preliminary patient- and provider-reported data on effectiveness outcomes (e.g., PC knowledge), PC referrals (from the EHR), and will explore ways to improve effectiveness and equity outcomes (i.e., equitable reach of intervention) through semi-structured interviews with a purposive sample of mPal patients ( $n = 30-40$ ) and providers ( $n = 6$ ). See Study Schema for assessment timepoints.

#### 4.2 SCIENTIFIC RATIONALE FOR STUDY DESIGN

In line with best practices for pilot studies, we are testing feasibility, not formal hypotheses surrounding effectiveness outcomes. We are not randomizing provider and system-level strategies because 1) we do not plan to randomize providers in our next trial (rather, clinics will be randomized to start mPal at different times through a stepped-wedge design); and 2) intervention contamination would occur within the clinic.

#### 4.3 JUSTIFICATION FOR INTERVENTION

mPal was developed based on theory, preliminary studies that identified key determinants of PC implementation in outpatient asLC care, and preliminary data to develop specific mPal content with patient and provider feedback.

#### 4.4 END-OF-STUDY DEFINITION

A patient is considered to have completed the study if he or she has completed the baseline assessment and the follow-up (T2) assessment. A provider is considered to have completed the study if they complete the baseline assessment and the follow-up (T3) assessment. The end of the study is defined as completion of the follow-up (T2 for patients; T3 for providers) and completion of EHR extraction for follow-up outcomes..

### 5 STUDY POPULATION

#### 5.1 PATIENT INCLUSION CRITERIA

In order to be eligible to participate in this study, an individual must meet all of the following criteria:

1. new or recurrent AJCC stage IIIB-IV non-small cell lung cancer or extensive stage small cell lung cancer
2. 18 years of age or older
3. ECOG performance status 0-3/Karnofsky 40-100;
4. At least 3 weeks into active oncologic treatment
5. Receiving treatment at Markey Cancer Center

Rationale: We chose to recruit at least one month after starting treatment to allow patients time to begin treatment and experience treatment-related side effects.

#### 5.2 PATIENT EXCLUSION CRITERIA

An individual who meets any of the following criteria will be excluded from participation in this study:

1. Unstable brain metastases (i.e., progressive neurological deficits, inadequately controlled seizures, or requiring escalating steroid doses);
2. Cognitive (i.e., dementia) or psychiatric condition (e.g., psychotic disorder) for which participating would be inappropriate
3. Receiving palliative care
4. Unable to speak and read English.

### 5.3 PROVIDER INCLUSION CRITERIA

In order to be eligible to participate in this study, an individual must meet all of the following criteria:

1. Oncologist
2. Advanced practice providers and nurses who work with enrolled oncologists
3. Provides care at least a half day a week to advanced stage lung cancer patients at Markey Cancer Center

Note: Fellows will be allowed to participate in this study.

### 5.4 PROVIDER EXCLUSION CRITERIA

An individual who meets any of the following criteria will be excluded from participation in this study:

1. Unable to speak and read English.

### 5.5 SCREEN FAILURES

Screen failures will be defined as patients who consent to participate in this study but are not subsequently assigned to the study intervention due to ineligibility or are assigned to intervention, but do not meet eligibility criteria and are withdrawn by investigators. Patients who do not meet the criteria for participation in this trial because of meeting one or more exclusion criteria that are likely to change over time may be rescreened. Examples include improvement in functional status and a progression of disease or disease recurrence for which a patient will begin treatment for advanced stage disease. Rescreened participants will be assigned the same participant number as for the initial screening.

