## 6.3 MEASURES TO MINIMIZE BIAS: RANDOMIZATION AND BLINDING

This is a randomized controlled trial design (patient-level randomization). Study staff and patients will not be blinded to allocation; however, study staff and patients will not know allocation until after a patient has completed the baseline questionnaire. The statistician will generate the randomization table, which will be implemented through REDCap.

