### 10.4 STATISTICAL ANALYSES

#### 10.4.1 GENERAL APPROACH

We will use descriptive statistics (means, standard deviations, median, range) to examine the distribution of continuous variables. We will calculate 95% CIs for each of the feasibility measures to determine the range of estimates that are consistent with our data.

We will use one-sample negative binomial probabilities and tests of binomial proportions to compare to hypothesized values. We will summarize reasons for ineligibility and refusal and compare patients who drop out or do not adhere by demographic and clinical characteristics. Ordinal scaled variables such as feasibility and acceptability will be compared between groups

before and after baseline (as well as change from baseline) using the Wilcoxon Rank Sum statistic. Within group comparison of the pre versus post baseline measures will be evaluated using the Wilcoxon Signed Rank statistic.

We will use qualitative methods to analyze patient and provider feedback from the exit interviews and descriptive statistics to summarize participants' acceptability, feasibility, and appropriateness ratings of the intervention. The interviews will be transcribed verbatim and managed in ATLAS.ti or other qualitative software for analysis. The PI and study coordinator will code interviews by domains (e.g., perceived impact of mPal on clinical care, barriers, facilitators to using mPal, suggested changes to improve equity of mPal). Data will be analyzed using thematic content analysis to describe perceptions.

Statistical significance will be indicated by  $p < .05$ .

---

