#### 10.4.2 ANALYSIS OF THE PRIMARY ENDPOINT(S)

The primary outcome of the feasibility is enrollment ( $\geq 60\%$ ). A one-sample binomial test will be used to compare the observed enrollment percentage to 60%.

Enrollment (primary): Number of patients enrolled divided by the number of eligible patients approached

Retention: The percentage of patients and providers who complete baseline and follow-up questionnaires.

Acceptability: Mean post-treatment patient and provider ratings  $\geq 3.5/5$  on intervention acceptability, feasibility, and appropriateness (psychometrically validated measure; Table 2), and a brief semi-structured interview to explore factors associated with acceptability.

---

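### Section 5.5 relabels patients already assigned to the intervention as screen failures, which can remove mPal patients from retention and the between-arm comparisons and leaves their place in the enrollment rate undefined

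*Combined protocol and SAP*

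**What the plan says.** Section 5.5 defines screen failure in two limbs. The first covers patients who consent and are then not assigned because they are ineligible. The second covers those who "are assigned to intervention, but do not meet eligibility criteria and are withdrawn by investigators". No time limit is attached to the second limb, and it does not except patients who have already viewed mPal.

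The same section says that patients who fail screening "because of meeting one or more exclusion criteria that are likely to change over time may be rescreened", and adds: "Rescreened participants will be assigned the same participant number as for the initial screening".

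Section 6.3 puts allocation after the baseline questionnaire and states: "Study staff and patients will not be blinded to allocation". It does not say what happens to the allocation of a rescreened patient.

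Section 8.2 lets an investigator discontinue any participant, in either arm, who meets an exclusion criterion that is newly developed or was missed at entry. Patients who consented but did not receive the intervention may be replaced; those who received it and then leave may not.

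Section 10.3 describes the analysis samples only by their sizes (40 and 40). Section 10.4.2 defines the primary endpoint as "Number of patients enrolled divided by the number of eligible patients approached", and retention as the percentage completing baseline and follow-up questionnaires. Section 10.4.3 compares pre-post change between arms by t-tests.

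**The concern.** Screen failure normally ends at randomisation. Here a label that usually means never in the trial can be given to someone who has consented, given baseline data and been allocated, by staff who know the allocation. Three things are at stake.

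- **Between-arm comparison.** The second limb names patients assigned to the intervention and has no counterpart for usual care. With no all-randomised population, a relabelled mPal patient can leave the Section 10.4.3 comparison while a usual-care patient with the same eligibility error has no such route under 5.5.
- **Retention.** A withdrawn mPal patient is a non-completer. Once called a screen failure, the same patient may not be counted at all.
- **Enrollment.** Section 10.4.2 does not say when a patient becomes enrolled, or whether a screen failure stays in the numerator, the denominator or both.

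In addition, rescreening is not limited to patients who have not yet been allocated. The plan is therefore silent on whether a returning patient keeps the first allocation.

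**Working it through.** **Inputs.** 80 patients, 40 per arm (Sections 1.1, 10.2, 10.3). Criterion of at least 60% for enrollment and for retention (Section 3). Planned test: "A one-sample binomial test will be used to compare the observed enrollment percentage to 60" percent, at p < .05 with sidedness not stated (Sections 10.4.1, 10.4.2). The plan gives no number approached, no precision target and no frequency of late-found ineligibility, so 80 cannot be re-derived and the size of the effect can only be illustrated.

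**Assumption.** 133 eligible patients approached. This is the largest number for which 80 enrolled meets the criterion: 80/133 = 60.2%, 80/134 = 59.7%.

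**Enrollment rate with k relabelled patients**

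| k | Kept: 80/133 | Removed from both: (80 − k)/(133 − k) | Numerator only: (80 − k)/133 |
|---|---|---|---|
| 0 | 60.2% | 60.2% | 60.2% |
| 1 | 60.2% | 79/132 = 59.8% | 79/133 = 59.4% |
| 4 | 60.2% | 76/129 = 58.9% | 76/133 = 57.1% |
| 8 | 60.2% | 72/125 = 57.6% | 72/133 = 54.1% |

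The shift per patient is 60.15 − 59.85 = 0.3 points if removed from both counts, and 1/133 = 0.75 points if removed from the numerator only.

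**How narrow the boundary is (removal from both counts).** The criterion changes from met to not met only at 133 approached for k = 1 or 2 (at 132, k = 2 gives 78/130 = 60.0%, still met), at 132–133 for k = 3, and at 131–133 for k = 4.

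**Binomial test.** At 80/133 the exact 95% CI is 51.3% to 68.5%, a half-width of about 8.6 points, and the two-sided exact p against 60% is 1.00. At k = 8, p is 0.585 (both counts) or 0.184 (numerator only). The test is not significant in any of these cases. It has its own boundary at a higher enrollment rate: 80/115 = 69.6% gives p = 0.036, and two removals from both counts give 78/113 = 69.0% with p = 0.055. That too needs an assumed number approached lying at the edge.

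**Retention, for illustration.** Suppose 80 are randomised and 47 complete follow-up: 47/80 = 58.8%, below the criterion. Relabelling one non-completing mPal patient gives 47/79 = 59.5%; relabelling two gives 47/78 = 60.3%, which meets it.

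**Between-arm comparison.** Each relabelled patient is 1/40 = 2.5% of the mPal arm. The direction and size of the bias cannot be computed, because the plan gives no standard deviation or expected difference.

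**5.5 and 8.2 side by side.** An mPal patient whose missed exclusion criterion is found after viewing the video is a screen failure under 5.5, with no bar on rescreening. Under 8.2 the same patient is an investigator discontinuation who is not to be replaced. A usual-care patient with the same error falls, on the literal wording, only under 8.2. Neither section refers to the other on this point.

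**The case against.** The strongest reply is that several of the consequences are not in the text, and much of it is right.

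- A reader might infer that the primary endpoint is made to depend on events after allocation. The plan does not say so. Section 10.4.2 never states that screen failures leave either count. A patient who was ineligible at entry does not belong among eligible patients approached, so removal from both counts corrects the rate; what comes late is the discovery. A true dependence on later events would arise only if the newly developed criteria of 8.2 fed into 5.5. Receiving palliative care is an exclusion criterion and referral to it is an anticipated effect of mPal (Sections 5.2, 6.4), so that route should be closed, but neither section opens it.
- A reader might infer that one patient could be randomised twice. No section provides for this. The rescreening examples in 5.5 are states before entry, and keeping one participant number points to a single record. This is a gap, not a procedure.
- A reader might infer that ineligible usual-care patients must stay in. Section 8.2 contradicts that, since discontinuation is open in both arms. The wording of 5.5 may also mean allocated to either arm.
- Pre-screening against the health record (Section 5.6) should make late discovery uncommon, and the enrollment example sits at a chosen boundary.

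What the reply does not remove: 5.5 does give the label after allocation, unblinded staff apply it, its literal wording covers one arm, and no analysis population holds the patient in place. Discontinuing a patient under 8.2 and treating that patient as never having entered are different things for the analysis.

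**Conclusion.** The concern holds in a limited form. Section 5.5 states a rule that can take mPal patients out of the retention count and the between-arm comparison after allocation is known, and it leaves their place in the enrollment rate open. The main weight lies on the first two, at 2.5% of the arm per patient; how many patients would be affected is unknown.

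For the primary endpoint the effect is small: about 0.3 points per patient if removed from both counts. It decides the 60% criterion only when the rate lies at the threshold, under an assumed 133 approached, and there it leaves the binomial test unchanged. Dependence of the endpoint on post-allocation events and double randomisation are possibilities that the text fails to exclude. They are not things it prescribes.

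The change is worth making because it is cheap and because a feasibility trial whose primary result is a count should settle who is counted before allocation is known.

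**What to change.** 1. **Section 5.5.** Limit screen failure to consented patients found ineligible before randomisation, and delete the post-assignment limb. State that a randomised patient may not be randomised again and counts once.
2. **Section 10.3.** Define an all-randomised population: every randomised patient stays in the allocated arm for retention and for the comparisons in 10.4.3. Add a sensitivity analysis that omits patients ineligible at entry from both arms.
3. **Section 12.1.5.** Record eligibility errors found after randomisation as protocol deviations, in the same way in both arms, and report them by arm.
4. **Section 10.4.2.** Fix enrolled at one point, either consent or randomisation. Choose one arm-neutral rule in advance: patients ineligible on pre-randomisation information are either kept in both numerator and denominator or removed from both, with the other version as a sensitivity analysis. Criteria that develop after enrollment never change the count. Simply counting known ineligible patients as enrolled, with no such rule, would sit badly with a rate defined on eligible patients.
5. **Section 8.2.** Reconcile it with 5.5, so that one event has one name and discontinuation does not by itself remove a patient from the analysis.

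The cost is a short amendment touching these five sections, with no new data collection beyond logging the deviations. The downside is that a few ineligible patients remain in the between-arm analysis; the sensitivity analysis shows how much they matter.

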### 5.6 STRATEGIES FOR RECRUITMENT AND RETENTION, PARTICIPANT COMPENSATION

#### **Recruitment and Enrollment.**

As in prior work, we will use two primary recruitment strategies: direct patient referral from oncologists and providers at the Markey Cancer Center and review of patient (per report of patients coming to clinic with diagnostic codes for advanced stage lung cancer) and provider

appointment schedules at the MCC. Additional eligibility checks may need to occur from within the UKHC medical record. Study personnel will identify upcoming oncology appointments of patients pre-screened for eligibility. Study personnel will then recruit patients in person at clinic appointments, by telephone, Zoom, or through MyChart® after confirming with the oncology team that it is okay to approach the patient.

We are requesting a waiver of HIPAA authorization for recruitment purposes. This waiver will allow us to review appointment schedules at the MCC to pre-screen potential patients for eligibility through the electronic health record. Patients will be pre-screened for documentation in their EHR for inclusion and exclusion criteria.

**Inclusion of Women and Minorities.** Men and women of all races and ethnicities who meet the above-described eligibility criteria are eligible to participate in this study. We expect approximately 42% of participants to be women. Translating this to our sample size estimate of 80, we plan to enroll at least 33 women. We expect to enroll racially and ethnically diverse patients in proportions that reflect our catchment area (87% White, 9% Black or African American, <2% Hispanic, <1% Asian, <1% Native American).

**Retention.** We will use previous retention strategies, including reminding patients of study visits, and offering sessions and assessments when they are in clinic for care.

**Participant Compensation.** Patients will receive a \$20 gift card for completing the baseline assessment (T0), \$10 for T1 survey, \$10 for the T1 interview (mPal only), \$30 for the 8-week follow-up (T2), and \$10 for the T2 interview (mPal only). Providers will have the option to accept \$20 gift cards for completing T0 (baseline), \$10 for T1 (post mPal viewing), \$20 for completing T3 (~3 months post-mPal implementation) surveys; and \$30 for the interview.

## 6 STUDY INTERVENTION

### 6.1 STUDY INTERVENTION ADMINISTRATION

#### 6.1.1 STUDY INTERVENTION DESCRIPTION

**Theoretical Model and Implementation Strategies Underlying mPal.** mPal is based in the application of the Capability, Opportunity, Motivation Model of Behavior (COM-B) and the Behavior Change Wheel. The COM-B distills 14 theory-based constructs that explain behavior (e.g., knowledge, beliefs about capabilities, environmental resources) into three domains. Capability refers to a person's mental and physical ability to engage in a behavior (e.g., knowledge); motivation to the processes energizing and directing behavior; and opportunity to factors beyond a person that enable a behavior. The Behavior Change Wheel specifies intervention functions (e.g., education) that target the COM-B constructs. The COM-B/BCW model has been used to develop interventions and study their implementation in healthcare. mPal's multilevel implementation strategies were selected using the Expert Recommendations for Implementing Change list of strategies and Preliminary Studies.

**mPal Content and Procedures.** See attachments for intervention content. Operational details of the mPal intervention appear in Table 1. mPal's patient content can be delivered either through MyChart via a "MyChart questionnaire" or a web-based tool (developed with Markey Cancer Center in UK IRB# 63922). The mPal patient content is comprised of two components: (1) a one-time educational video and knowledge check questions that seek to educate patients about palliative care; and (2) a palliative care needs screener (e.g., symptom concerns, psychological, spiritual) with questions about whether patients would like to meet with palliative care or discuss palliative care and their palliative care needs with their oncology provider. Procedures for viewing the mPal patient educational tool will vary based on whether a patient has MyChart. Patients with MyChart will be sent a research message requesting they complete mPal roughly two days before their next clinic appointment. They can complete this either in clinic on a tablet with study staff or from home. Patients who do not have a MyChart account will view Markey's web-based tool on a tablet with study staff in clinic or through a personal link provided via REDCap. Patients responses to the mPal palliative care needs screener and desire for palliative care will be entered in their electronic health record for their oncology provider to view. As part of the intervention, study staff will distribute the Markey Cancer Center palliative care FAQ document to participants that indicate yes to wanting more palliative care information on the mPal tool. The delivery methods for this document include email, mail, in-person distribution, or distribution through MyChart or EPIC as part of an after-visit summary.

After patients complete the initial palliative care screener, it will be re-administered to patients at future oncology treatment visits up to 3 times over the 3-months following receipt of the mPal educational component, though patients will have the option to request to continue to take the screener as part of their cancer care. The screener can be readministered via MyChart, in-person via tablet, or in-person through the Welcome™ function in EPIC® at visit check-ins. If patients request to re-review the mPal education, it will be provided to them.

mPal's provider content includes a web-based tool that provides education on: 1) Evidence for PC, clinical guidelines, and practice standards; 2) Education about common misconceptions of PC/provider reported barriers; 3) PC resources available in their clinic; 4) mPal's patient and provider-facing procedures/content; and 5) case examples showing the use of mPal in PC discussions during LC care.

**Table 1. Detailed Description of mPal**

Function	Forms tested	ERIC Implementation Strategies 	Operational Details
Education – to target PC knowledge; motivation to use PC	
Patient:
 
 
• Web-based tool
 
 
Provider:
 
 
• Web-based tool/recording presentation
 
	
Patient:
 
 
• Distribute educational materials
 
• Prepare patients to be active participants in their care
 
 
Provider:
	
Patient: This tool will include: 1) a brief video describing PC; 2) an assessment of potential concerns to be addressed through PC (e.g., pain, worry about illness); 3) options to request a referral to PC and to talk with their oncology team about their concerns and about PC.
 
Timing: Delivered 3 weeks after starting LC treatment to allow symptoms/concerns to emerge; PC screener readministered at cancer treatment/oncologist appointments up to 3 times in the 3-months after receiving the education component.
 
Provider: Oncology providers will view a 15-20-minute mPal tutorial (recording presentation) online at the time of their choosing.
 
Presentation will review: 1) Evidence for PC, clinical guidelines, and

		
 
Distribute educational materials
 
	practice standards; 2) Education about common misconceptions of PC/provider reported barriers; 3) PC resources available in their clinic; 4) mPal's patient and provider-facing procedures/content; and 5) case examples showing the use of mPal in PC discussions during LC care. Timing: Delivered one month before the patient-level intervention starts.
Incentivization – to increase provider motivation to use PC	Provider: 
 
Patient PC needs from web-based tool populate in EHR along with clinical guideline alert
 
Performance reports
 
	Provider: 
 
Facilitate relay of clinical data to providers
 
Remind providers
 
Audit and feedback
 
	Providers- Once a patient completes mPal, the patient's PC needs will populate in the EHR. This information can be pulled directly into the clinical encounter note. Timing: PC alerts will occur whenever a patient uses the mPal web-based tool.
Environmental Restructuring – to increase opportunities to use PC	System: 
 
Referral template
 
EHR tool to identify high need patients
 
	System: 
 
Facilitate relay of clinical data to providers
 
Make billing easier
 
	System: To increase patient and provider opportunities to use PC, we will program: 1) an EHR/provider-facing alert for patients whose mPal web-based tool assessment indicates high need for PC (e.g., multiple PC concerns, poor performance status); 2) a structured PC referral template providers can use.

PC = palliative care; ERIC = Expert Recommendations for Implementing Change; EHR = electronic health record

